#### 24.8 Final Analysis

The final analysis will be performed to report a primary CSR based on a data cut off after all 60 patients in the planned efficacy evaluation population have completed tumor assessment within 24 weeks by the investigator per RECIST v1.1

Since patient will be treated until they met one of the discontinuation criteria, some patients may still be ongoing at the time of final analysis. Therefore, a long-term follow-up study can be performed after final analysis with all available data (no cut-off date applied).

#### 25.0 GENERAL STUDY MANAGEMENT INFORMATION

#### 25.1 Informed Consent

The Investigator will provide for the protection of the patients by following all applicable regulations. These regulations are available upon request from the Sponsor. The Informed Consent Form used during the informed consent process must be reviewed by the Sponsor and approved by the IRB/IEC.

Before any procedures specified in the protocol are performed, a patient must:

- Be informed of all pertinent aspects of the study and all elements of informed consent
- Be given time to ask questions and time to consider the decision to participate
- Voluntarily agree to participate in the study
- Sign and date an IRB/IEC approved Informed Consent Form

### 25.2 Institutional Review Board and Institutional Biosafety Committee Approvals

An Institutional Review Board (IRB), which is operating in accordance with Title 21 of the Code of Federal Regulations Part 56, must approve the clinical protocol and corresponding informed consent form and agree to monitor the conduct of the trial and review its progress at regular intervals. Before the Sponsor or its designate will make investigational product available, and before the trial begins, the investigator will provide to the Sponsor documented evidence of IRB approval, demonstrating review and approval of this clinical protocol, and informed consent form.

An Institutional Biosafety Committee (IBC), which is duly registered with the NIH Office of Biotechnology Activity (NIH/OBA) in accordance with NIH Guidelines, must approve the

clinical protocol. The investigator will provide to the Sponsor documented evidence of IBC approval prior to initiation of the clinical trial.

### 25.3 **Pre-Study Documentation**

The Investigator must provide the Sponsor with the following documents BEFORE enrolling any patients:

- Completed and signed form 1572
- All applicable country-specific regulatory forms
- Current, dated curricula vitae for the Investigator, Subinvestigators, and other individuals having significant investigator responsibility who are listed on the Form 1572 or equivalent, or the clinical study information form.
- Copy of the IBC approval letter
- Copy of the IRB/IEC approval letter for the protocol and informed consent. All
  advertising, recruitment, and other written information provided to the patient must be
  approved by the IRB/IEC. Written assurance of continuing approval (at least annually)
  as well as a copy of the annual progress report submitted to the IRB/IEC must also be
  provided to the Sponsor.
- Copy of the IRB/IEC-approved Informed Consent Form to be used
- Where applicable, a list of the IRB/IEC members or a FWA/DHHS number
- Copy of the protocol sign-off page signed by the Investigator
- Copy of the current medical license (online verification is also acceptable) of the Principal Investigator, any Subinvestigators and any other individuals having significant responsibility as listed in the 1572
- Fully executed Clinical Trial Agreement (CTA)
- Where applicable, a financial disclosure form for the Principal Investigator and any other persons listed in the 1572
- A written document containing the name, location, certification number, and date of certification of the laboratory to be used for laboratory assays and those of other facilities conducting tests. This document should be returned along with the 1572. The

Sponsor must be notified if the laboratory is changed or if any additional laboratory is to be used.

• List of normal laboratory values and units of measure for all laboratory tests required by the protocol. This is required for each laboratory to be used during the study. The Sponsor must be notified if normal values or units of measurement change.

# 25.4 Protocol Amendments

Any significant change in the study requires a protocol amendment. An Investigator must not make any changes to the study without IRB/IEC and Sponsor approval. All protocol amendments must be reviewed and approved following the same process as the original protocol.

### 25.5 Direct Access, Data Handling, and Record Keeping

#### 25.5.1 Confidentiality

All study-related laboratory and clinical data gathered in this protocol will be stored in a password-protected database. All patient information will be handled using anonymous identifiers. Linkage to patients' study data is only possible after accessing a password-protected database. Access to the database is only available to individuals directly involved in the study.

Patient personal health information that is accessed for this study will not be reused or disclosed to any other person or entity, or for other research.

### 25.5.2 Case Report Forms (CRFs)

The Investigator will permit study-related monitoring, audits, IRB/IEC review, and regulatory inspections by providing direct access to source data and documents.

All study-related information will be recorded on source documents. All required data will be recorded in the CRFs. All CRF data must be submitted to the Sponsor throughout and at the end of the study.

The Clinical Research Coordinator (CRC), or other properly trained site personnel, will complete the CRFs as soon as possible upon completion of the study visit; the Investigator will review and approve the completed CRFs.

The information collected on CRFs shall be identical to that appearing in original source documents. Source documents will be found in the patient's medical records maintained by site

personnel. All source documentation should be kept in separate research folders for each patient.

In accordance with federal regulations, the Investigator is responsible for the accuracy and authenticity of all clinical and laboratory data entered onto CRFs. The PI will approve all completed CRFs to attest that the information contained on the CRFs is true and accurate.

All source documentation will be available for review/monitoring by the Sponsor (or designee) and regulatory agencies.

The Principal Investigator will be responsible for ensuring the accurate capture of study data. At study completion, when the CRFs have been declared to be complete and accurate, the database will be locked. Any changes to the data entered into the CRFs after that time can only be made by joint written agreement among the Study Chair, the Trial Statistician, and the Protocol Project Manager.

#### 25.5.2.1 Records Retention

The Investigator shall retain and preserve one copy of all data generated in the course of the study, specifically including but not limited to those defined by GCP as essential, for the longer of: (i) 3 years after the last marketing authorization for the study drug has been approved or 3 years after study completion or (ii) such longer period as required by applicable global regulatory requirements. At the end of such period, the Investigator shall notify the Sponsor in writing of its intent to destroy all such material. The Sponsor shall have 30 days to respond to the Investigator's notice, and the Sponsor shall have a further opportunity to retain such materials at the Sponsor's expense.

### 25.5.3 Oversight and Monitoring

The Sponsor (or designee) will be the monitoring entity for this study. The data will be checked for completeness and correctness in real-time online and during scheduled site monitoring visits.

Discrepancy reports will be generated and transferred to the study center for resolution by the Investigator or his/her designee.

The Sponsor (or designee), in collaboration with all participating Investigators, will routinely review all adverse events and suspected adverse reactions considered "serious". The Sponsor

(or designee) will audit study-related activities to ensure that the study is conducted in accordance with the protocol, local standard operating procedures, FDA regulations, and Good Clinical Practice (GCP). Significant findings will be communicated to the site Investigator and, as applicable, the local IRB. For additional information, please refer to the Clinical Monitoring Plan and Safety Monitoring Plan.

### 25.6 Study Suspension, Termination, and Completion

The Sponsor may suspend or terminate the study or any part of the study at any time for any reason. If the Investigator suspends or terminates the study, the Investigator must promptly inform the Sponsor and the IRB/IEC and provide a detailed written explanation. The Investigator will also return all study-specific investigational treatment agents (i.e. GX-188E, pembrolizumab), study-specific equipment (e.g., TDS-IM ® Electroporation Device), containers, and other study materials to the Sponsor or designee, unless specific permissions and instructions have been provided for on-site destruction of the materials. Upon study completion, the Investigator will provide the Sponsor, IRB/IEC, and regulatory agency with final reports and summaries as required by regulations.

#### 26.0 **Protection of Human Patients**

#### 26.1 Protection from Unnecessary Harm

Each clinical site is responsible for protecting all patients involved in human experimentation. This is accomplished through the IRB mechanism and the process of informed consent. The IRB reviews all proposed studies involving human experimentation and ensures that the subject's rights and welfare are protected and that the potential benefits and/or the importance of the knowledge to be gained outweigh the risks to the individual. The IRB also reviews the informed consent document associated with each study in order to ensure that the consent document accurately and clearly communicates the nature of the research to be done and its associated risks and benefits.

#### 26.2 **Protection of Privacy**

Patients will be informed of the extent to which their confidential health information generated from this study may be used for research purposes. Following this discussion, they will be asked to sign the HIPAA form and informed consent documents. The original signed document will become part of the patient's medical records, and each patient will receive a copy of the

signed document. The use and disclosure of protected health information will be limited to the individuals described in the informed consent document.

APPENDIX 1: SCHEDULE OF EVENTS (SCREENING -WEEK 10)

	g .	Treatment Week						
	Screening (-28 to 0)	Week 1 Day 1	Week 2 Day 1 (± 3 days)	Week 3Day 1 (± 3 days)	Week 4 Day 1 (± 3 days)	Week 7 Day 1 (± 3 days)	Week 10 Day 1 (± 3 days)	
Informed Consent	X							
Demographics	X							
Medical History 	X							
Physical Exam  and Vital Signs 	X	X	X	X	X	X	X	
Performance Status (ECOG)	X				X	X	X	
Moore Criteria Risk Categorization 	X							
Adverse Events 		X	X	X	X	X	X	
Concomitant Medications 	X	X	X	X	X	X	X	
CBC (w/diff, platelet count) 	X	X	X	X	X	X	X	
Serum Chemistry 	X	X	X	X	X	X	X	
Serology  , Chest X-ray, ECG	X							
Thyroid Function Tests and CEA/TA4 	X					X		
Urinalysis 	X	X					X	
Coagulation Assessment 	X						X	
Pregnancy Test 	X							
Research Blood Collection 14	X	X			X	X	X	
GX-188E Vaccinationn (i.m.)		X	X 		X 	X		
Pain Assessment 		X	X		X	X		
Pembrolizumab (i.v.)		X			X	X	X	
Tumor Biopsy Sample 	X						X	
Radiographic Evaluation of Tumor Burden 	X						X	

### GX-188E/Pembrolizumab [Protocol Number: GX-188E-005] Amended (V4.0)\_29Aug2022

- 1. Medical history includes any significant comorbid conditions requiring active treatment as well as surgeries and therapies related to the treatment of malignancies, including cervical cancer. Cervical cancer history includes review of prior treatments and documentation of HPV-16 or -18 positivity. Medical records and/or local laboratory results will be considered adequate documentation HPV-16 or -18 positivity
- 2. Screening and End of Study require a complete physical exam. For all other study, physical exams should be symptom-directed and clinically significant findings reported as adverse events.
- 3. Vitals to include heart rate, respiratory rate, temperature, blood pressure (systolic and diastolic) weight, and height. Height only required at screening
- 4. Determine whether the patient has low risk, mid risk or high risk disease based upon Moore criteria (See Appendix 3).
- 5. Adverse event monitoring begins once a patient receives the first dose of study treatment and continues until 28 days after the last administration of study treatment, or until the initiation of a new anti-cancer therapy, whichever occurs first. For Serious Adverse Events (SAEs), follow up will continue for 90 days.
- 6. Concomitant medication is defined as any prescription or over-the-counter preparation, including vitamins and supplements. All concomitant medications from 28 days before Day 1 through the end of the subject's study participation must be recorded. (During the follow-up period after the end of the clinical trial, only the data about the antineoplastic therapy (surgical therapy, chemotherapy, radiation therapy, etc.) treated after the end of the subject's study participation is recorded.)
- 7. CBC w/differential to include: Hemoglobin, Platelets, Red Blood Cells, White Blood Cells, Basophils (%)), Eosinophils (%)), Lymphocytes (%), Neutrophils (Abs) and Hematocrit.
- 8. Serum Chemistry at Screening to include: Sodium, Potassium, CO2 or bicarbonate, Chloride, Albumin, Alkaline Phosphatase, ALT, AST, Total Bilirubin, Blood Urea Nitrogen, Calcium, Creatinine, Glucose, Magnesium, Phosporus, Total Protein, LDH, and Cockcroft-Gault calculated Creatinine Clearance. At all other time points, only a basic metabolic panel (Na, K, CO2 or bicarbonate, Cl, Ca, BUN, creatinine & glucose) plus AST and ALT are required. Other tests may be ordered as clinically indicated. However, if subjects had the result of serum chemistry tests at the screening which met the all in/exclusion criteria and the investigators judged that the result of same tests at W1D1 were no clinical significance, they can be enrolled.
- 9. Serology at Screening to include: HIV Ag/Ab, HAV Ab (IgM), HBV Ab, HBV sAg, HCV Ab, HCV RNA (HCV real time PCR)
- 10. Includes thyroid-stimulating hormone (TSH), free thyroxine (FT4), and T3. Thyroid function tests and CEA/TA4 levels will be performed approximately every 6 weeks.
- 11. Urinalysis is only required at Screening, Week 1 Day 1, Week 10 Day 1, and End of Study. Urinalysis should be ordered as clinically indicated at any other timpoint.
- 12. Coagulation assessment includes: prothrombin time, partial thromboplastin time, and international normalized ratio (PT/PTT/INR). Coagulation assessments are only required at Screening and End of Study. On-treatment coagulation assessments (e.g., Week 10) are only required if a biopsy is planned and must be evaluated within 24 hours prior to biopsy collection on the same day.
- 13. All females of child-bearing potential must have a negative serum or urine pregnancy test within 3 days prior to the first dose of study treatment.
- 14. Blood collection. Samples will include serum for immune response Flt-3L(Screening, Week10, Week22, Week49 then after every 27 weeks) and whole blood for PBMC T cell responses(Screening, Week1, Week4, Week7, Week10, Week16, Week22, Week49 then after every 27 weeks). Samples obtained at all time points associated with study treatment administration, except for Screening, should be obtained prior to administration of either/both agents. Blood sample for Flt-3L will be collected at screening visit, week 10, week 22, week 49 and every 27 weeks thereafter.
- 15. Pain assessment using a 0-10 numeric pain rating scale will be administered prior to and 5 minutes (± 2 minutes) following each GX-188E electroporation procedure
- 16. All patients must submit either an archival tumor tissue sample OR fresh biopsy sample at Screening. Biopsies will be evaluated for bio-markers using immunohistochemistry but not limited to it. Patients with biopsy-accessible lesions will be asked to provide an optional biopsy sample at approximately Week 10 (or End of Study if the patient discontinues prior to Week 10) for paired biopsy analysis.

# GX-188E/Pembrolizumab [Protocol Number: GX-188E-005] Amended (V4.0)\_29Aug2022

[figure not shown]
17. Radiographic evaluations of tumor burden by RECIST v1.1 will be performed by a blinded independent central reviewer at Screening, approximately every 9 weeks during the treatment period, or more frequently as clinically indicated, and at End of Study if the reason for discontinuation is other than for confirmed radiologic disease progression. Scans obtained within 28 days prior to Week 1 Day 1 will be accepted for Screening and do not need to be repeated unless a clinically significant difference is suspected. Confirmatory scans are required approximately 4 weeks after any scan that indicates either an objective response, stable disease or disease progression,

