## STATISTICAL METHODS

Maximum 60 patients are planned for enrollment into this clinical trial.

Safety Analysis. All patients who receive at least one dose of the investigational treatment will be included in the safety population. All safety analyses will be performed on the safety population. Adverse Events (AE) will be coded according to the MedDRA adverse event dictionary. The results will be tabulated to examine their frequency, organ systems affected, and relationship to study treatment. The results of laboratory tests will be evaluated similarly.

Efficacy Analysis. Efficacy results, including but not limited to ORR24, BORR, DOR, DCR, TTR, PFS, and OS for patients enrolled into Part A will be provided using descriptive statistics. Objective responses will be evaluated according to both RECIST v1.1 and Response Evaluation Criteria In Solid Tumors for Immunotherapeutics (iRECIST).

Note: Confirmatory scans are required for all determinations of objective response (PR or CR), Stable disease(SD) and disease progression (PD). Confirmatory scans must be performed at least 4 weeks later.

Part B follows a Simon Two-Stage mini-max design. The sample size for the first stage of Part B is 15 patients; the sample size for the second stage is 13 patients, for a total of 28 patients. Patients from Part A without a DLT, who receive the recommended Phase 2 treatment regimen and who are considered evaluable for efficacy will be included in the analysis for Part B Stage 1. For a null hypothesis ORR24 of 0.15 and an alternative hypothesis ORR24 of 0.35, the sample size of 28 subjects will provide a one-sided significance level of 5% and a power of 80%. For Stage 1, a minimum of three patients must demonstrate a response (PR or better) to proceed to the second stage. Study has passed the first stage of Simon-Two stage design. If Stages 1 and 2 are completed, a minimum of 8 patients must demonstrate a response (PR or better) to reject the null hypothesis. If a patient's responses could not be confirmed, that patient will not be included in the primary efficacy population for ORR24.

Part C is to evaluate efficacy in larger patient population.

In Keynote-158 study (pembrolizumab monotherapy in patients who have progressed with standard of care systemic therapy), ORR in total patients (i.e. regardless of PD-L1 status) and with CPS  $\geq 1$  were 12.2% and 14.6%, respectively.

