# 22.1.2 **Tumor Imaging During the Study**

The first on-study imaging assessment should be performed approximately 9 weeks ( $\pm 3$  days]) from the date of treatment initation. Subsequent tumor imaging should be performed every 9 weeks ( $\pm 3$  days at Week 19,  $\pm 7$  days for subsequent timepoints) or more frequently if clinically indicated. Imaging timing should follow calendar days and should not be adjusted for delays

in cycle starts. Imaging should continue to be performed until disease progression is identified by the investigator (unless the investigator elects to continue treatment and follow iRECIST), the start of new anticancer treatment, withdrawal of consent, or death, whichever occurs first. All supplemental imaging must be submitted to the central imaging vendor.

Objective response and stable disease should be confirmed by a repeat imaging assessment. Tumor imaging to confirm SD, PR or CR should be performed at least 4 weeks after the first indication of a response is observed. Participants will then return to regular scheduled imaging, starting with the next scheduled imaging time point. Participants who receive additional imaging for confirmation do not need to undergo the next scheduled tumor imaging if it is less than 4 weeks later; tumor imaging may resume at the subsequent scheduled imaging time point. Note: Response does not typically need to be verified in real time by the central imaging vendor.

Per iRECIST (Appendix 6 and Section 22.3), disease progression should be confirmed by the site 4 to 8 weeks after site-assessed first radiologic evidence of PD in clinically stable participants. Participants, who have unconfirmed disease progression may continue on treatment at the discretion of the investigator until progression is confirmed by the site, provided they have met the conditions detailed in Section 22.3. Participants who receive confirmatory imaging do not need to undergo the next scheduled tumor imaging if it is less than 4 weeks later; tumor imaging may resume at the subsequent scheduled imaging time point, if clinically stable. Participants, who have confirmed disease progression by iRECIST, as assessed by the site, will discontinue study treatment. Exceptions are detailed in Section 22.3.

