#### APPENDIX 5: RECIST CRITERIA VERSION 1.1

Source: Eisenhauer et al., 2009

Sponsor's Note: Confirmatory scans are required approximately 4 weeks after any scan that indicates either an objective response or disease progression

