# **Evaluation of best overall response**

The best overall response is the best response recorded from the start of the study treatment until the end of treatment taking into account any requirement for confirmation. The patient's best overall response assignment will depend on the findings of both target and non-target disease, will also take into consideration the appearance of new lesions and will depend upon confirmatory scans. For this study, determinations of either CR, PR or PD require a confirmatory scan at least 4 weeks later. This is described further in Table B below.

Table B.Best Overall Response

Target Lesions	Non-Target Lesions	New Lesions	Overall Response	Best Response for this Category Also Requires
CR	CR	No	CR	≥4 weeks confirmation
CR	Non-CR/ Non-PD	No	PR	≥4 weeks confirmation
PR	Non-PD	No	PR	
SD	Non-PD	No	SD	documented at least once ≥4 weeks from baseline
PD	Any	Yes or No	PD	
Any	PD*	Yes or No	PD	no prior SD, PR or CR
Any	Any	Yes	PD	

\* In exceptional circumstances, unequivocal progression in non-target lesions may be accepted as disease progression

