#### **15.1.** PRIMARY EFFICACY ENDPOINTS

The primary efficacy variable is BICR-assessed ORR24 by RECIST 1.1 in Part B and C.

Best overall response within 24 weeks (BOR24) is the best objective response achieved within the first 24 weeks of treatment prior to study discontinuation. All available response designations will contribute to the BOR24 determination. If a patient's BOR24 could not be confirmed, that patient will not be included in the primary efficacy population for ORR24. Additional patients will be enrolled to meet the study hypothesis. Any CR or PR must be confirmed by a sequential assessment that is at least 4 weeks apart. The confirmation rule is defined in Table 2 (please refer to RECIST 1.1 [1]). The confirmed response will be determined before analysis. The number and percentage of patients in each category of best overall response CR, PR, SD, PD or Not Evaluable (NE) will be provided.

ORR24 is the proportion of efficacy evaluable patients who achieve an objective response (PR or CR) within 24 weeks prior to study discontinuation. The number and percentage of patients who achieve best overall response of PR or CR will be summarized.

If the first responses can be confirmed by the second response within 24 weeks of treatment. they will be included as responses for ORR24. Also, If the first response within 24 weeks is confirmed by the second response after 24 weeks of treatment, the first response should be included as response for ORR24.

Table 2. Best overall response when confirmation of CR and PR is required per RECIST 1.1 Guideline

Overall response  First time point	Overall response Subsequent time point	Best overall response
CR	CR	CR
CR	PR	PR, or SD provided at least 28 days' duration, otherwise PD a
CR	SD	SD provided at least 28 days' duration, otherwise PD

Document: \(\)\ieedc-vnac01\\Biosdata\\Genexine\\GX-188E\\GYA02599\\Biostatistics\\Documentation\\SAP\)

Author: [name] Version Number: 1.1

Version Date: 05Sep2022

Template No: CS TP BS016 Revision 6 Reference: CS WI BS005

Analysis Plan Page 29 of 48

CR	PD	SD provided at least 28 days' duration, otherwise PD
CR	NE	SD provided at least 28 days' duration, otherwise NE
PR	CR	PR
PR	PR	PR
PR	SD	SD
PR	PD	SD provided at least 28 days' duration, Otherwise PD
PR	NE	SD provided at least 28 days' duration, Otherwise NE
NE	NE	NE

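### The protocol gives two timings for the confirmatory scan, approximately 4 weeks and at least 4 weeks; a scan on day 25 to 27 fits the first but cannot by itself confirm a response for ORR24

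*Protocol*

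**What the plan says.** Three places in the protocol give an approximate interval. Footnote 17 of the first Schedule of Events table (Appendix 1) reads "Confirmatory scans are required approximately 4 weeks after any scan that indicates either an objective response, stable disease or disease progression", and footnote 15 of the second table repeats it. The sponsor's note at the head of Appendix 5 reads "Confirmatory scans are required approximately 4 weeks after any scan that indicates either an objective response or disease progression". None of the three attaches a window.

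Three other places in the protocol set a minimum:

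- Synopsis, Statistical Methods: "Confirmatory scans must be performed at least 4 weeks later".
- Section 22.1.2, the imaging instruction to sites: "Tumor imaging to confirm SD, PR or CR should be performed at least 4 weeks after the first indication of a response is observed".
- Appendix 5, evaluation of best overall response: "For this study, determinations of either CR, PR or PD require a confirmatory scan at least 4 weeks later".

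The SAP uses only the minimum. Section 15 repeats the synopsis rule, and section 15.1 says "Any CR or PR must be confirmed by a sequential assessment that is at least 4 weeks apart". No tolerance is given for an early scan. Section 15.1 also removes a patient whose best response within 24 weeks could not be confirmed from the primary ORR24 population.

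Two further statements in SAP 15.1 soften this: "All available response designations will contribute to the BOR24 determination", and "If the first response within 24 weeks is confirmed by the second response after 24 weeks of treatment, the first response should be included". Under protocol section 22.1.2 imaging continues every 9 weeks by calendar day, and the next scheduled scan may be skipped only when it falls less than 4 weeks after the confirmatory one.

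**The concern.** Protocol section 16 sends the reader to Appendix 1 for the procedures in table form, and the visits tabulated there carry windows of 3 days or 1 week either side. A scan at 25, 26 or 27 days is therefore a natural reading of the footnotes. It satisfies them and fails the rule that defines the primary endpoint.

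What is at stake is a responder counted as unconfirmed because of scan timing and not because of her disease. Under SAP 15.1 she can leave both the numerator and the denominator of ORR24. A mistimed scan cannot be repaired afterwards, so the wording matters before the scans are booked.

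**Working it through.** **1. The plan's own figure.** Inputs from protocol section 24.3: N = 60, 25% dropout, null 12.2%, alternative 37%, success if the two-sided 95% Clopper-Pearson lower limit exceeds 12.2%. Evaluable patients: 60 × (1 − 0.25) = 45. The lower limit for x responders in n is the 2.5% quantile of Beta(x, n − x + 1). At n = 45 it is 11.20% for x = 10 and 12.88% for x = 11, so 11 responders are needed. P(X ≥ 11 | 45, 0.37) = 0.974, which reproduces the stated 97% power. This point disputes no sample-size figure.

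**2. Day count.** Week k Day 1 is day 1 + 7(k − 1), so scans fall on day 64 (Week 10), day 127 (Week 19) and day 190 (Week 28). Twenty-four weeks is 24 × 7 = 168 days.

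| First response | Early scan (25 days later) | Next scheduled scan | Days after early scan | Days after first response |
|---|---|---|---|---|
| 64 | 89 | 127 | 38 | 63 |
| 127 | 152 | 190 | 38 | 63 |

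The early scan fails the 28-day rule. In both rows the next scheduled scan is at least 28 days after the early one, so it is still due, and at 63 days after the first response it qualifies to confirm. In the second row it falls after day 168, which SAP 15.1 accepts.

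With the section 22.1.2 windows at their extremes, the gap from the first response to the next scheduled scan is still 63 − 3 − 3 = 57 days (Week 10 to Week 19) or 63 − 3 − 7 = 53 days (Week 19 to Week 28). Only in the second case, with an early scan at day 27, does the remaining gap fall below 28 days (53 − 27 = 26). That scan could then be skipped and confirmation would wait for the following one.

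**3. When the response is lost.** Take PR on day 64, PR on day 89 and PD on day 127. No pair of PR scans is 28 days apart, so the response is unconfirmed. Had the second scan been on day 92 and still PR, it would have counted. The same happens if she stops imaging or is not evaluable before a qualifying scan. It also happens if the word sequential in SAP 15.1 is read as the immediately next scan only, which the subsequent-time-point column of SAP Table 2 does not rule out.

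**4. Effect of one lost responder at the boundary.**

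| Result | Lower limit | Exceeds 12.2%? |
|---|---|---|
| 11/45 | 12.88% | yes |
| 10/44 (patient excluded) | 11.47% | no |
| 10/45 (patient kept as non-responder) | 11.20% | no |
| 14/60 | 13.38% | yes |
| 13/59 (patient excluded) | 12.29% | yes |
| 13/60 (patient kept as non-responder) | 12.07% | no |

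The excluded rows follow the text of SAP 15.1. The kept rows follow SAP Table 2, which reclassifies an unconfirmed CR or PR as SD, PD or NE.

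**5. Illustration of size.** The documents give no frequency, so suppose a fraction f of responses is lost and counted as non-response. Power is P(X ≥ r | n, 0.37(1 − f)).

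| f (assumed) | n = 45, r = 11 | n = 60, r = 14 |
|---|---|---|
| 0 | 97.4% | 99.2% |
| 5% | 95.5% | 98.3% |
| 10% | 92.5% | 96.5% |
| 20% | 82.1% | 88.8% |

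**The case against.** A reader might infer that any scan a few days early voids a true response. The documents do not support that. Scheduled imaging continues, all response designations count, and confirmation after week 24 is accepted, so a patient who stays in response and keeps being scanned is normally recovered. That part of the objection stands in full.

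A reader might also infer that the protocol tells sites one thing and the SAP another. That too is more than the text shows: sites are told at least 4 weeks in the synopsis, in section 22.1.2 and in Appendix 5 itself. The conflict lies within the protocol; the SAP agrees with the stricter half.

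The 11/45 example is a boundary case. At the design rate 0.37 × 45 = 16.65 responders are expected, exactly 11 has probability of about 2.7%, and 17/45 falling to 16/44 leaves the lower limit at 22.4%. The final analysis is planned on 60 efficacy-evaluable patients (protocol 24.8, SAP 4.3), where exclusion under SAP 15.1 does not reverse the result. SAP 15.1 also provides for enrolling additional patients, so the denominator need not stay reduced. Removing unconfirmed patients from the population is a separate issue that better wording of the scan interval would not settle.

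What survives is narrow: two instructions conflict, the looser one sits in the Schedule of Events, and some responders will have no later qualifying scan.

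**Conclusion.** The inconsistency is real and touches the primary endpoint, but its reach is limited. A confirmatory scan at 25 to 27 days meets the Schedule of Events and cannot by itself confirm a CR or PR. The response is lost only when no later qualifying scan shows response, or under the narrowest reading of sequential. How often that would happen is unknown, and the power figures above rest on assumed loss rates.

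One lost responder changes the conclusion only at the boundary. At 45 evaluable, 11 responders becoming 10 turns success into failure. At 60 evaluable, 14/60 becoming 13/59 remains a success; 13/60, if the patient is kept as a non-responder, misses the interval criterion. No sample size, significance level or stated power is wrong. The correction is worth making because it costs almost nothing and cannot be made after the scans are taken.

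**What to change.** 1. For response and stable disease, replace the approximate interval in Appendix 1 (footnote 17 of the first table, footnote 15 of the second) and in the Appendix 5 sponsor's note, so far as each covers them, with the rule already in the synopsis, section 22.1.2 and the SAP: at least 4 weeks, that is 28 days or more.
2. The same notes also cover progression, for which sections 22.1.2 and 22.3 give 4 to 8 weeks under iRECIST. These passages must be reconciled. Because they bear on stopping treatment, the choice of interval is for the sponsor and investigators.
3. Add a sentence to SAP 15.1 that any later qualifying scan, not only the next one, can confirm a response.

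The cost is one phrase in three places, one SAP sentence and a note to sites. No design figure changes.
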